Cranial Electrotherapy Stimulation on Acute Stress

Study Protocol

Document version: February 24, 2023

IRB Approval date: April 19, 2023

PROTOCOL TITLE:

Cranial Electrotherapy Stimulation (CES) Influences on Acute Stress Responses

PRINCIPAL INVESTIGATOR (PI):

Name: [name]

Department: Center for Applied Brain and Cognitive Sciences

Are you a student? Yes No

If Yes, you must designate a Faculty Advisor below.

FACULTY ADVISOR (required for Student PIs):

Name: N/A

Department: N/A

VERSION NUMBER/DATE

Version 1/ February 24 2023

1.0 Purpose of the study:

The purpose of this study is to quantify the effects of 20 sessions of (Active vs Sham) Cranial Electrotherapy Stimulation (CES) on multiple measures of acute stress responses: biochemical (salivary alpha amylase and cortisol), physiological (e.g., heart rate, heart rate variability, respiration rate), emotional (state anxiety), and behavioral (i.e., cognitive task performance).

2.0 Background / Literature Review / Rationale for the study:

Acute Stress

Soldiers are continually exposed to acute stressors during training and operations, activating a cascade of biochemical changes in the body, including an initial sympathetic-adrenal medulla (SAM) catecholamine-related response, and a slower-moving hypothalamic-pituitary-adrenal (HPA) glucocorticoid-related response (Angelova et al., 2021; Axelrod & Reisine, 1984; Buchheim et al., 2019; Charmandari et al., 2005; Gagnon & Wagner, 2016; McEwen, 2007; Padgett & Glaser, 2003). The diverse effects of acute stress on neurotransmitters and the central nervous system are associated with similarly diverse perceptual and cognitive effects, generally related to the intensity of experienced stress and the processes demanded by specific mental tasks. For example, mild-to-moderate acute stress can improve performance on relatively basic (or well-learned and rehearsed) perceptual and cognitive tasks, such as simple reaction time and verbal memory retrieval, perhaps owing to activation of the ascending reticular activating system (ARAS) (Arnsten, 2009; Broadbent, 1971; Brunyé et al., 2021a, 2021b; De Cicco et al., 2018; Hupbach & Fieman, 2012; Shields et al., 2019). Moderate-to-high acute stress, in contrast, can negatively influence performance on tasks more demanding of executive processes and spatial memory retrieval, perhaps owing to HPA-related activation and brain regions (e.g., prefrontal cortex, hippocampus) with high glucocorticoid receptor densities (Arnsten, 1998, 2009; Brunyé et al., 2016, 2019; Cerqueira et al., 2007; Luine et al., 1994; Olver et al., 2015; Richardson & VanderKaay Tomasulo, 2011; Shields et al., 2015, 2016).

Individuals engaged in high-stakes occupations, such as military personnel, first responders, and emergency medicine physicians, are continually exposed to moderate-to-high stress, which can negatively influence their ability to sustain performance on job-related duties (Meredith et al., 2011; Orasanu & Backer, 1996; Reynolds & Wagner, 2007; Sood et al., 2011). As a result, scientists and practitioners alike seek methods to reduce the stress response and increase resilience to its short- and long-term effects. This includes efforts to train emotion regulation strategies, resilience, mindfulness, and biofeedback (Berking et al., 2010; Jha et al., 2015; Kennedy & Parker, 2019; Reivich et al., 2011). Methods also include non-invasive brain stimulation, including transcranial direct current stimulation (tDCS), transcranial alternating current stimulation (tACS), transcranial magnetic stimulation (TMS), and cranial electrotherapy stimulation (CES). Each of these techniques has received attention for its potential utility in altering biochemical and physiological manifestations of acute stress responses and thus altering behavior.

Cranial Electrotherapy Stimulation

Cranial electrotherapy stimulation (CES) differs from transcranial electrical stimulation (tES) in several ways. First, CES electrodes include one anode and cathode but are

typically attached to the temples, mastoids, or earlobes (rather than the scalp). Second, CES is typically administered using alternating rather than direct current, at relatively low intensities ranging from 50-500 μ A and frequencies ranging from 0.5 to 100 Hz. Third, rather than targeting specific brain regions, CES is thought to exert nonspecific effects on both the central and peripheral nervous systems. Many mechanistic explanations regarding CES effects on the central and peripheral nervous systems, neurotransmitters and hormones, and emotion and behavior have been proposed (see Brunyé et al., 2021a, 2021b). Regarding central and peripheral nervous system effects, various publications have proposed that CES influences sympathetic versus parasympathetic drive, alters oscillatory brain activity, increases cerebral blood flow in subcortical brain regions, stimulates afferent projections of the vagus and/or trigeminal nerve, and modulates functional brain connectivity and plasticity. Regarding neurotransmitter and hormonal effects, studies have variably proposed that CES alters SAM and HPA axis and associated neurotransmitters such as cortisol, serotonin, norepinephrine, dopamine, acetylcholine, and γ -aminobutyric acid (GABA) (Barclay & Barclay, 2014; Datta et al., 2013; Ferdjallah et al., 1996; Kavirajan et al., 2014; Lee et al., 2019; McClure et al., 2015; Roh & So, 2017; Schroeder & Barr, 2001; Wagenseil et al., 2018; Winick, 1999; Yennurajalingam et al., 2018). Unfortunately, no comprehensive model of CES provides mechanistic linkages between these putative effects of CES or provides compelling associations to behavioral outcomes.

According to computational models of CES current propagation, CES has the strongest neuromodulatory effects on diverse cortical and subcortical brain regions including the temporal lobes, medulla oblongata, midbrain, thalamus, hypothalamus, pons, and insula (Datta et al., 2013; Ferdjallah et al., 1996). In research examining brain activity with electroencephalography (EEG) during and after CES administration, some studies find evidence for alpha and beta band power modulation, suggesting that CES may be expected to influence arousal states and attention (Lee et al., 2019; Schroeder & Barr, 2001; Wagenseil et al., 2018). Finally, two studies have examined brain hemodynamics during and after CES administration, using both functional magnetic resonance imaging (fMRI) and xenon-enhanced computed tomography (XeCT). In the fMRI study, the authors found that CES induced broad regional brain deactivation and altered default mode network activity and proposed that CES may induce transient downregulation of rumination or worry (Hamilton et al., 2011). In the XeCT study, the authors found that CES altered cerebral blood flow (CBF) specifically in the brainstem and thalamus, suggesting that CES plays a role in modulating anxiety and pain perception (Gense de Beaufort et al., 2012).

In addition to its effects on functional brain activity, CES has also been found to modulate salivary, urinary, blood, or cerebrospinal fluid (CSF) levels of stress hormones, inflammation and immune markers, and neurotrophic factors. These studies find highly mixed results. For example, while most studies suggest that CES does not influence serotonin, dopamine, β -endorphins, alpha amylase, cortisol, adrenocorticotrophic hormone (ACTH), C-reactive protein, interleukin-1, or interleukin-6 (Cho et al., 2016; Krupitsky et al., 1991; Roh & So, 2017; Yennurajalingam et al., 2018), an earlier study suggested that CES administration decreases cortisol and increases ACTH, serotonin, and β -endorphins (Liss & Liss, 1996). Note that the latter study shows a high risk of bias, with experimenters testing themselves as participants, financial conflicts of interest, and a lack of random assignment or blinding to CES conditions (Brunyé et al., 2021a, 2021b; Kavirajan et al., 2014).

In clinical contexts, CES devices are classified as class II (special controls) medical devices for the treatment of anxiety or insomnia and as class III medical devices for the treatment of depression (Docket No. FDA-2014-N-1209). In one of the largest placebo-controlled CES studies to date, active (versus Sham) CES (100 μ A, 0.5 Hz, 35 days of treatment) was administered to 115 participants with an anxiety disorder; results showed an approximately 32% reduction in anxiety measured using the Hamilton Rating Scale for Anxiety (HAM-A-17) (Barclay & Barclay, 2014). However, results are generally mixed about CES effectiveness in treating clinical insomnia (Feighner et al., 1973; Lande & Gragnani, 2013; Wagenseil et al., 2018; Weiss, 1973) and depression (Kavirajan et al., 2014; McClure et al., 2015; Mischoulon et al., 2015).

In our own recent study (Brunye et al., 2022), we used a double-blind, placebo-controlled, crossover design to examine the effects of CES on emotional, physiological, biochemical, and behavioral responses to acute stress. Healthy male participants visited the laboratory for two sessions, one involving active CES administration (100 μ A, 0.5 Hz, 20 min administration) and one involving Sham, inactive CES. During each session, participants were placed under stress (threat of torso shock) while performing challenging cognitive tests, and we measured emotional, biochemical (alpha amylase, cortisol), physiological (heart rate, respiration rate, heart rate variability, pupil diameter), and cognitive behavioral (memory, decision-making, spatial orienting) responses. Outcome metrics were compared using repeated measures analysis of variance (ANOVA) and planned comparisons. The stress induction reliably modulated measures of sympathetic adrenal medullary (SAM) activity but not hypothalamic–pituitary–adrenal (HPA) axis activity. Active versus placebo CES did not significantly influence any emotional, biochemical, or physiological outcome measure; there was, however a consistent numerical pattern wherein active CES did appear to reduce some of the physiological responses to stress relative to Sham CES. Furthermore, active CES did selectively increase performance on a recognition memory test and degrade performance on a perceptual decision-making test; however, overall performance on our cognitive tasks was very low, suggesting a potential floor effect that could be masking any additional effects of CES. Overall, our study found very limited evidence that CES reliably modulates the acute stress response.

The Present Study

The present study is designed to extend our recent study in three primary ways.

First, rather than a fixed intensity of CES (100 μ A), we will use a standardized procedure to identify each participant's sensory threshold (Bystritsky et al., 2008; Gong et al., 2016; Schroeder & Barr, 2001). Because 100 μ A was consistently sub-threshold (i.e., imperceptible) in our prior participants, it is likely this procedure will result in higher (e.g., 250-500 μ A) CES intensities administered. There are three primary reasons why we have chosen to use higher intensity CES, and why we believe it will make it more likely to find CES effects on physiology, biochemistry, and behavior:

1. Two extant research studies suggest that 300 μ A (Bystritsky et al., 2008; Overcash et al., 1989) and up to 1500 μ A (Smith et al., 1994) are effective at lowering anxiety, in line with the conclusions of a review examining CES effects on anxiety and stress (De Felice, 1997).
2. Most of the data from our prior research with the device shows the predicted pattern of results, for example lower heart rate variability and respiration rate with CES (vs sham); however, the pattern is numerical only and does not reach traditional significance levels. We believe that higher intensity CES may

amplify these previously noted patterns; of course, this is an empirical question and cannot be answered without additional data collection.

3. This procedure of individualized thresholding is congruent with manufacturer's recommendations, and they report seeing the most reliable anxiolytic-like effects with this procedure. Also, the procedure of individualized thresholding and minimum intensity ($\geq 250\mu\text{A}$) is congruent with the Special Operations Command's (SOCOM) current use of the device during military training and operations, where they report anecdotal success for stress mitigation.

Second, rather than a single 20-minute session of CES administration, we will use daily administration (20-minutes/day) over the course of 4-6 weeks.

These first two modifications are being made to better conform with the device manufacturer's (Electromedical Products International, Inc., Mineral Wells, TX) recommendations for CES administration.

Finally, to elicit a more robust stress response that activates both SAM and HPA activity, we will increase the intensity (to level 3 of 5) of our torso shock administration. With these changes, we make four primary hypotheses:

H1: Biochemistry: We hypothesize that Active vs Sham CES will reduce biochemical responses to stress, including salivary alpha amylase as an indicator of SAM activity and salivary cortisol as an indicator of HPA activity.

H2: Physiology: We hypothesize that Active vs Sham CES will reduce physiological responses to stress, including heart rate, heart rate variability, respiration rate, and pupil diameter.

H3: Emotion: We hypothesize that Active vs Sham CES will reduce subjective experiences of stress, including responses on the STAI.

H4: Behavior: We hypothesize that Active vs Sham CES will lead to increased performance on tasks typically degraded by stress exposure, including a recognition memory test and a spatial memory test.

3.0 Participant Population:

We expect to recruit up to 500 individuals, including Soldiers and civilians, to achieve a final sample size of 40 complete data sets. Our high recruitment number allows for Soldier group briefings (active-duty units at their home station and HRV cohorts at DEVCOM SC) which are routinely 30+ and can be upwards of 100 Soldiers.

We anticipate an approximately 40-50% attrition rate given our requirement to meet a minimum CES threshold of $300\mu\text{A}$ (i.e., a $250\mu\text{A}$ minimum CES intensity) and the prolonged study duration. To accommodate the potentially high attrition rate, we expect to recruit and consent up to 500 Soldiers and/or civilians, and schedule and enroll up to 100 Soldiers and/or civilians.

We are recruiting civilians in addition to military personnel because we have limited access to military personnel to conduct this research, and we have no a priori reason to believe that civilians will show markedly different stress responses, task performance, or CES responses relative to military personnel. In fact, most extant research examining the utility of CES for stress reduction is conducted with civilians. Because one of our tasks (marksmanship) could be considered geared towards military personnel, see

Section 15 for a description of possibly increased risk of psychological harm to civilians versus military personnel.

We will recruit participants 18-40 years of age, or 17 years if emancipated minor. This age range was chosen to represent the majority of Active Duty enlisted military personnel, which is under 41 years of age (*Defense, 2014*). There is no gender-based enrollment restriction.

Inclusion Criteria: Eligible individuals include those who:

1. Can sit and stand freely.
2. Have not used or experienced CES administration in the past.
3. Agree to have their data stored in a repository (database) for future use. Peer-reviewed scientific journal may require data to be stored in a repository as a condition for publication. Such repositories are online databases, in which coded data is linked (no link to participants personally) to the journal article citation.

Exclusion Criteria: The following exclusion criteria will be evaluated by self-report (on the Informed Consent Form) prior to beginning the study.

1. Use of prescription medications, other than oral contraceptives, as they may alter stress hormones (Granger, Hibel, Fortunato, & Kapelewski, 2009).
2. Women only:
 - a. Pregnant or plan to become pregnant during the study, as the shock belt may be unsafe for pregnant women and their children.
 - b. Nursing, as it may alter stress hormones (Ahn & Corwin, 2015).
3. History of:
 - a. A neurological or psychological disorder (such as depression, anxiety disorders, migraines, cluster headaches, seizures, Post-traumatic stress disorder (PTSD) or panic attacks). Individuals with neurological and psychological disorders may exhibit altered stress responses, not representative of the population (Spijker & van Rossum, 2012).
 - b. Cardiac disease (including arrhythmia or fast or skipped heart beats). The shock belt may be unsafe for individuals with cardiac disease (Steptoe & Kivimäki, 2012)
 - c. Implanted medical devices, such as pacemakers. The Shock belt may be unsafe for individuals with an implanted medical device.
 - d. Hypertension. The Shock belt may be unsafe for individuals with diagnosed hypertension (Spruill, 2010). This risk is low, and the prevalence of undiagnosed hypertension in our targeted cohort (ages 18-40) is also very low; for these reasons, we believe self-report of diagnosed hypertension is sufficient.
 - e. Insomnia, as insomnia is associated with chronic physiological arousal (Bonnet & Arand, 2010)
 - f. Head injury (including neurosurgery, concussion, TBI, skull fracture, hematoma)
 - g. Illness that caused brain injury
 - h. Any other brain-related condition (such as traumatic brain injury)

- i. Metal in the head (outside of mouth, such as shrapnel, surgical clips, or fragments from welding or metalwork)
- j. Implanted medical device (e.g., pacemaker, insulin pump)

Study Withdrawal Criteria:

We have five study withdrawal criteria, related to minimum CES intensities, failing to meet minimum performance during the criterial learning tasks, intolerance for torso shock, self-reported symptoms on the Daily Participant Questionnaire (Appendix A), and intolerance for CES.

First, during the individualized baselining phase (part of the Thresholding and Baselining session), if a participant does not reach our minimum CES intensity of 250µA (i.e., a 300µA minimum threshold), they will be dismissed from the study.

Second, during the baseline or follow-up session, if a participant cannot reach the accuracy criterion during the criterial learning tasks within 5 study-test cycles, they will be dismissed from the study.

Third, during the baseline or follow-up session, if a participant cannot tolerate the torso shock (psychologically or physically), we will reschedule their session for a different day. If during two consecutive sessions they cannot tolerate the level 3 intensity, they will be dismissed from the study.

Fourth, at the beginning of any CES session, if the participant answers a 3 or higher (on the scale from 1-4) to any of the Daily Participant Questionnaire items, their session will be rescheduled for a different day. If they report 3 or higher for any of these questions for two consecutive sessions, they will be dismissed from the study.

Fifth, during any CES session, if a participant cannot tolerate the CES administration at their individualized intensity (i.e., answering ≥ 3 to a single item on the “presence and intensity” *and* “relation to stimulation” sections), they will receive secondary CES stimulation as described in the Procedures section (6.0). If their reported symptoms do not successfully subside (i.e., falling below a 3 rating) after the secondary stimulation, and this occurs for two consecutive sessions, they will be dismissed from the study.

Each of these study dismissal criteria are described in more detail in the Procedures section (6.0), and detailed in the Appendix E flowchart.

4.0 Special Populations:

- Children
- Fetuses/Neonates
- Prisoners
- Members of the military
- Non-English speakers
- Those unable to read (illiterate)
- Employees of the researcher
- Students of the researcher

- Adults lacking capacity to consent and/or adults with diminished capacity to consent, including, but not limited to, those with acute medical conditions, psychiatric disorders, neurologic disorders, developmental disorders, and behavioral disorders
- Disadvantaged in the distribution of social goods and services such as income, housing, or healthcare
- Fear of negative consequences for not participating in the research (e.g. institutionalization, deportation, disclosure of stigmatizing behavior)
- Approached for participation in research during a stressful situation such as emergency room setting, childbirth (labor), etc.

5.0 Research Locations and Sample Size:

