5.2 Sample Size

Sample size estimation was based on effect sizes from Barclay & Barclay (2014) who found that CES reduced subjective anxiety with an effect size of $f = 0.47$. Using GPower, the total sample size was estimated to be 38 to achieve power of 0.80 with an alpha criterion of 0.05. Our goal is therefore 40 complete data sets, with 20 participants in each of the two groups.

6.0 Procedures Involved:

We will use a double-blind, placebo-controlled design with random assignment of participants to one of two experimental groups: Active versus Sham CES. Two versions of the critical learning and virtual reality tasks have been developed (Brunyé & Giles, 2023; used in DEVCOM Armament Center IRB protocol 18-007, Tufts University protocol 1808016), and will be used herein, in balanced order across participants.

Military participants will be transported to and from the CABCS research performance site in Medford, MA, for participating in the baseline and follow-up session. If overnight accommodations are required for Soldiers, those will be provided along with other travel related items (e.g., per diem). Travel will be planned by the research team and coordinated with unit leadership (if troop request) or HRVPO (if HRVs). Civilian participants will not be provided with transportation, accommodations, or any other travel-related compensation.

All non-disposable devices used in the protocol will be disinfected in accordance with Occupational Health and Safety Administration and Centers for Disease Control

guidance, and product label instructions, paying attention to the required personal protective equipment and the contact time needed to achieve disinfection. In addition, all frequently touched surfaces in the research area, such as workstations, countertops, and doorknobs will be cleaned between participants.

Upon scheduling, participants will be randomly assigned to the Active or Sham CES condition, using the [=rand()] function in Microsoft Excel. All participants will complete a Thresholding & Baseline session, the CES administration sessions, and then a Follow-up session.

Testing Day 1: Thresholding & Baseline

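### The shock-belt safety exclusions are checked once, at consent; the available text has no re-check before the second shock session about 4 to 7 weeks after the first

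*Protocol*

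**What the plan says.** Protocol Section 3.0 lists the exclusions and says how they are established: "The following exclusion criteria will be evaluated by self-report (on the Informed Consent Form) prior to beginning the study". Section 10.0 confirms that the screening questions sit in the consent form.

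Four exclusions carry a belt-safety reason. Item 2a reads "Pregnant or plan to become pregnant during the study, as the shock belt may be unsafe for pregnant women and their children". Items 3b (cardiac disease), 3c (implanted devices) and 3d (hypertension) give the same kind of reason. For 3d the protocol adds that the risk is low and that self-report of a diagnosis is enough.

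Section 6.0 fixes the belt at level 3 and triggers it on errors during cognitive testing. Follow-up uses the Baseline procedures apart from thresholding, so the shock task is given a second time.

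The rules for stopping someone are in Section 3.0: "We have five study withdrawal criteria, related to minimum CES intensities", plus the learning criterion, shock tolerance, symptoms on the Daily Participant Questionnaire, and CES tolerance. The shock rule is that "if a participant cannot tolerate the torso shock (psychologically or physically), we will reschedule their session for a different day", with dismissal after two consecutive failures. Under Section 16.0, data from withdrawn participants are destroyed and not analysed.

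**The concern.** The protocol judges the belt possibly unsafe for four groups and applies that judgement once, although completers face the belt at least twice. All four conditions can arise after consent: an unplanned pregnancy, a new cardiac or hypertension diagnosis, or a newly implanted device. Staff who follow the written procedure have no step at Follow-up that would detect the change, and no instruction on what to do if they learn of it.

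What is at stake is participant safety at the second exposure. The goal of 40 complete data sets implies at least 40 such exposures. The documents give no rate at which these exclusions are newly met, and none is assumed here.

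**Working it through.** **Size of the hazard, from the protocol's own figures.** Section 15.0 gives a maximum belt output of 92 mJ against a health-risk threshold of 5000 mJ. 92 / 5000 = 0.0184, so the output is 1 − 0.0184 = 98.2% below the threshold. This agrees with the protocol's statement of more than 98%.

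**Time between the two shock sessions.** The plan states no figure, so it is built from Section 6.0: 20 sessions on weekdays, up to six weeks, and Follow-up within 5 days of the last session. The gap from Baseline to the first CES session is not given and has to be assumed.

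- Shortest: the first CES session is assumed to be on the next weekday after Baseline. 20 sessions / 5 per week = 4 weeks, so the last session is on day 28 after Baseline. Follow-up can come at about that time: 28 / 7 = 4.0 weeks.
- Longest, six calendar weeks of CES: 6 × 7 + 5 = 47 days from the first CES session, or 6.7 weeks. With an assumed 3-day gap after Baseline, 47 + 3 = 50 days, or 7.1 weeks.
- Longest, six Monday-to-Friday weeks: the sixth Friday is day 5 × 7 + 4 = 39 from the first CES session, and 39 + 5 = 44 days, or 6.3 weeks.
- If the six-week limit is meant to include Follow-up, the upper end is about 6 weeks. A Follow-up rescheduled for shock intolerance can fall later.

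So the interval is roughly 4 to 7 weeks. Time since screening is longer, because the gap from consent to Baseline is not stated.

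**Whether anything else in the text closes the gap.**

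- *Five withdrawal criteria (Section 3.0).* None names a newly met exclusion. The tolerance rule acts only once shocks have begun, and tolerance is a different matter from the stated concern: a newly pregnant participant may tolerate the shock well.
- *Daily Participant Questionnaire.* It is given at Baseline and so at Follow-up. Section 3.0 describes it as a report of symptoms on a 1-4 scale, and its reschedule-or-dismiss rule is written for CES sessions.
- *In-brief on travel (Section 10.0, item 2).* It is described as a further explanation of the study, not as screening, and appears only under the active-duty recruits.
- *Belt-risk information and opt-out (Section 15.0).* These are given in the consent form and rely on the participant to act.
- *Item 2a.* It covers a pregnancy planned during the study, not an unplanned one.
- *Rationale for 3d.* It defends self-report as a method and says nothing about when to ask.

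**Room for lost completers.** Section 3.0 says "We anticipate an approximately 40-50% attrition rate" and plans to "schedule and enroll up to 100 Soldiers and/or civilians". At the ceiling, 100 × (1 − 0.50) = 50 to 100 × (1 − 0.40) = 60 complete, which is 10 to 20 above the goal of 40. The margin is gone if enrolment is only 40 / 0.50 = 80 at 50% attrition, or 40 / 0.60 = 67 at 40%.

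**The case against.** The strongest reply is that the gap is inferred from pages that were not available. A re-check would naturally sit in the consent form, in the Daily Participant Questionnaire (Appendix A) or in the dismissal flowchart (Appendix E). The questionnaire is completed at the start of Follow-up, before the belt is put on, and its items may ask about changes in health. This stands as a limit. A reader might infer that the study never re-checks these conditions, and the documents do not support that. They support only that no re-check appears in the available text.

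A reader might also infer that a newly pregnant or newly diagnosed participant would necessarily be shocked. The protocol is silent on the case and does not direct a shock. Such participants have been told of the belt risk, may stop at any time, and see staff at up to 20 CES visits. Shocks also follow errors, so exposure is not automatic. They could be shocked, if they say nothing and do not opt out.

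Third, the hazard is small and the population is aged 18-40 (or 17 if emancipated) and already screened. That is correct and sets the weight of the point. It does not remove it: with the same output figures in hand, the protocol still chose to exclude these groups, and the same judgement applies at the second exposure.

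**Conclusion.** The point holds as a minor, optional safety improvement. The exclusions with a stated belt-safety reason (2a, 3b, 3c, 3d) are checked once by self-report at consent. The level 3 shock task is repeated roughly 4 to 7 weeks after Baseline, and nothing in the available text asks the questions again.

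This rests on two assumptions: that the consent form and Appendices A and E contain no re-check, and that CES starts within a few days of Baseline.

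Three wider inferences are not supported:

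- Item 3j repeats the implanted-device exclusion but gives no belt reason of its own, so it is not counted.
- Exclusion 1 (prescription medication) is justified by stress hormones rather than belt safety, so it is outside this point.
- Nothing here bears on the sample size, the analyses or the trial's conclusions.

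**What to change.** 1. Repeat the existing self-report questions for 2a, 3b, 3c and 3d before the belt is put on at Baseline, at Follow-up and at any rescheduled shock session. If Appendix A, Appendix E or the consent form already does this, a cross-reference in Section 3.0 is enough.
2. State in Section 3.0 that anyone newly meeting one of the four does not receive the shock. The protocol says "Upon scheduling, participants will be randomly assigned to the Active or Sham CES condition", so every such stop comes after assignment and its number should be reported by arm.
3. State in Section 3.0, consistently with Section 16.0, that the by-arm count is kept and whether data already collected from such a participant are retained.

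The cost is one short form, built from existing questions, at visits that already open with questionnaires, plus a few sentences of protocol text. The downside is a few lost Follow-up sessions. Without step 3 the loss is larger: if the participant is treated as withdrawn, Section 16.0 removes Baseline and all CES-session data as well. The 10 to 20 spare completers absorb this only if enrolment reaches the ceiling of 100.
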